5.1 Contraception requirements

Not applicable. Only women of non-childbearing potential will be included in this study.

5.2 Prohibited treatment

Use of the following medications is not allowed during the course of the study from screening (Visit 1) to the end of the study. Patients who are receiving such medication(s) will be excluded, or if ethically and clinically justified, the medication(s) should be gradually withdrawn at least seven days before Visit 2:

- ACE inhibitors, mineralocorticoid receptor antagonists (e.g. spironolactone or eplerenone), aliskiren, vasopressin receptor antagonists (e.g. tolvaptan), or oral alkalinizing agents (e.g. sodium and potassium citrate or Shohl's solution)
 - Note: Patients who discontinue their ACE-inhibitor and substitute with an angiotensin receptor blocker (ARB) may be eligible to be re-screened provided their medication regimen has been stable for at least 1 month and their renal function has been stable for at least 3 months.
- Chronic administration (defined as >3 days per week) of NSAIDs or COX-2 inhibitors. The long-term chronic use of aspirin for cardiovascular prophylaxis is allowed provided the total daily dose does not exceed 325 mg. Intermittent doses of NSAIDs or COX-2 inhibitors are allowed but must not be within 48 hours prior to any scheduled visit or assessment or serum creatinine.
- Use of other investigational drugs at screening or within 30 days or 5 half-lives of the drug at screening, whichever is longer, unless local health authority guidelines mandate a longer period.
- Treatment with any medication that is contraindicated in renally impaired patients
- IV contrast dyes such as that used for a radiologic procedure
- Recombinant human erythropoietin

The following medications are prohibited due to potential for pharmacokinetic drug-drug interactions: bupropion, efavirenz, ifosfamide (sensitive CYP2B6 substrates); amodiaquine, paclitaxel, pioglitazone, repaglinide (sensitive CYP2C8 substrates); celecoxib, glimepiride, phenytoin, warfarin (sensitive or narrow index CYP2C9 substrates); glyburide (CYP2C9 and OATP1B1 substrate); irinotecan (OATP1B1 & BCRP substrate); topotecan (BCRP substrate); methotrexate (OAT1/3, BCRP substrate), bosentan (OATP1B1 substrate), atazanavir, cyclosporine, eltrombopag, gemfibrozil, lopinavir, rifampin, ritonavir, saquinavir, tipranavir (OATP1B1/1B3 inhibitors); cimetidine, diclofenac, probenecid (OAT1/3 inhibitor).

All other prior non-study medications (not specifically contraindicated in the exclusion criteria) will be allowed, provided the patient has been on a standard treatment regimen (at least 4 weeks of the same dose) and the treatment is not planned to be changed during the course of the study.

5.3 Dietary restrictions and smoking

- In Part 1, no alcohol is permitted from the domiciling period until after Study Completion evaluation. In Part 2, no alcohol will be permitted during the domiciling period and starting 24 hours prior to and during study visits.
- Intake of xanthine (e.g. caffeine) containing food or beverages (i.e., coffee, tea, soda, chocolate) will be restricted to no more than 2 cups/day.
- Subjects can drink water *ad libitum*. To ensure adequate hydration for urine collections in Part 1, subjects are recommended to have a fluid intake of at least 240 mL every 4 hours during waking hours in addition to fluid taken with meals and medication.
- Subjects should be counseled to avoid consuming large portions of cooked meat in the 24 hours prior to laboratory assessments. This restriction will reduce the variability in serum creatinine assessments which can be falsely elevated by dietary meat intake. During the domiciling period in Part 1 and Part 2, meals will be outlined by the study center's dietician in accordance with nutritional guidelines for patients with chronic kidney disease and nutritional counseling from the subject's physician.

Subjects will follow a standard weight maintaining diet while domiciled. No food other than that specified in the protocol will be consumed at any time during confinement. Subjects should be advised to consume the entire contents of the meal provided.

Meals should be provided only after all study procedures including blood and urine collections scheduled for that time have been completed.

A copy of the diet with content and nutritional information (amount of protein, carbohydrates, fat and calories for each meal) will be provided to the Sponsor prior to study start upon request.

5.4 General restrictions

- In Part 1, no strenuous physical exercise (e.g. weight training, aerobics, football) for 7 days prior to dosing until after Study Completion evaluation.
- In Part 2, no strenuous physical exercise (e.g. weight training, aerobics, football) for 7 days prior to dosing until after Study Completion evaluation, particularly for the 48 hours prior to study visits.

6 Treatment

6.1 Study treatment

Details on the storage and management of study medication, randomization and instructions for prescribing and taking study treatment are outlined in Section 3 of the Site Operations Manual.

6.1.1 Investigational treatment

The Investigational drug LHW090 Corporate Confidential Information matching placebos will be prepared by Novartis and supplied to the investigator site as open labelled bulk supply for Part 1.

For Part 2, LHW090 and its matching placebo will be supplied as double blind patient packs.

6.2 Treatment arms

Part 1: Subjects will be assigned to one of the following 2 treatment arms in a ratio of 2:1:

- A: LHW090 daily for 4 days, followed by 4 days followed by 4 days
- B: Matching placebo

Part 2: Subjects will be assigned to one of the following LHW090 treatment arms or placebo in a ratio of 3:3:2:

- A: LHW090 once dailyB: LHW090 once daily
- C: Matching placebo

6.3 Permitted dose adjustments and interruptions of study treatment

Study drug dose adjustments are not permitted. Subjects should be reminded of the importance of study drug compliance and compliance should be monitored and recorded.

In Part 2, patients should be instructed to bring their study medications with them on visit days for pill counts. If a short treatment interruption becomes necessary for an important reason, the subject may resume the study treatment. However, drug interruption should end, if possible, at least 3 days prior to the next study visit. A drug interruption occurring for \geq 4 consecutive days or \geq 5 total treatment days during the outpatient phase of the study will be considered a protocol deviation.

In the event that a subject will be transitioned to an ACE inhibitor at the end of the study or after premature discontinuation of study medication, a minimum of 72 hours must transpire between the last dose of LHW090 and the first dose of ACE inhibitor. Consideration should also be given to the existing ARB treatment of subjects in the study; concomitant treatment with an ACE inhibitor and an ARB should be avoided according to current guidelines and in compliance with the applicable local prescribing information of renin angiotensin aldosterone system (RAAS) agents.

6.4 Treatment assignment

Randomization numbers will be assigned in ascending, sequential order to eligible subjects (see Site Operations Manual for details). The investigator will enter the randomization number on the CRF.

In Part 1, randomization numbers will be generated using the following procedure to ensure that treatment assignment is unbiased and concealed from subjects and investigator staff. A randomization list will be produced by or under the responsibility of Novartis Drug Supply Management, using a validated system that automates the random assignment of treatment arms to randomization numbers in the specified ratio. The randomization scheme for subjects will be reviewed and approved by a member of the Novartis Randomization Group.

In Part 2, at Visit 2, all eligible subjects will be randomized via Interactive Response Technology (IRT) to one of the treatment arms. The investigator or his/her delegate will contact the IRT after confirming that the subject fulfills all inclusion/exclusion criteria. The IRT will assign a randomization number to the subject, which will be used to link the subject to a treatment arm and will specify a unique medication number for the first package of investigational treatment to be dispensed to the subject.

A subject randomization list will be produced by the IRT provider using a validated system that automates the random assignment of treatment arms to randomization numbers. Once a patient is deemed eligible for enrollment into the study and ready for dosing, the next lowest available randomization number will be assigned. These randomization numbers are linked to the different treatment arms, which in turn are linked to medication numbers. A separate medication list will be produced by or under the responsibility of Novartis Drug Supply.

Management using a validated system that automates the random assignment of medication numbers to packs containing the investigational drug(s).

6.5 Treatment blinding

This is a sponsor-open, investigator and subject double-blind study: subjects, investigator staff, and persons performing the assessments will remain blind to the identity of study treatments according to the specifications provided in Appendix 1.

The identity of the treatments will be concealed by the use of study drugs that are all identical in packaging, labeling, schedule of administration, appearance, and odor.

Randomization data are kept strictly confidential, and are accessible only to authorized personnel (e.g. unblinded site staff (pharmacist or authorized designee at the site), unblinded sponsor staff (e.g. for drug resupply, unblinded monitor), and sample analysts), until unblinding of the trial as described in the table in the blinding table in Appendix 1.

The study statistician, the study programmer and other personnel involved in data analysis (e.g. biomarker expert) will have access to the randomization list for planned and unplanned interim analyses, and are allowed to share unblinded information with the rest of the clinical team as appropriate for internal decision purposes, as outlined in the blinding table in Appendix 1.

Corporate Confidential Information

Unblinding will occur in the case of patient emergencies (see Section 6.6), at the time of the interim analysis and at the conclusion of the study.

6.6 Emergency breaking of assigned treatment code

Emergency unblinding should only be undertaken when it is essential to treat the subject safely and efficaciously. Most often, study treatment discontinuation and knowledge of the possible treatment assignments are sufficient to treat a study subject who presents with an emergency condition. A complete set of emergency code break cards will be provided to the investigator site(s) and a complete set will be available at Novartis for Part 1 of the study. All code break cards must be retained until the end of the study and returned to Novartis. They must be stored in a secure place but be accessible in case of emergency. The investigator will receive a blinded code break card for each subject, with the details of drug treatment covered by a removable, scratch-off cover. In an emergency, the scratch-off cover can be removed to determine the treatment. The scratch-off covers are not to be removed for any reason other than an emergency. When the investigator removes the scratch-off cover he/she must note the date, time, and reason for removing it and retain this information with the case report form documentation. The unblinded treatment code should not be recorded on the CRF. The investigator must also immediately inform the Novartis local monitor that the code has been broken.

For Part 2, emergency code breaks are performed using the IRT. When the investigator contacts the IRT to unblind a patient, he/she must provide the requested patient identifying information and confirm the necessity to unblind the patient. The investigator will then receive details of the drug treatment for the specified patient and a fax confirming this information. The system will automatically inform the Novartis monitor for the site and the Clinical Trial Head that the code has been broken.

It is the investigator's responsibility to ensure that there is a procedure in place to allow access to the IRT/code break cards in case of emergency. If appropriate, the investigator will inform the subject how to contact his/her backup in cases of emergency when he/she is unavailable.

An assessment will be done by the appropriate site personnel and the sponsor after an emergency unblinding to assess whether or not study drug should be discontinued for a given subject and, if applicable, whether the subject can continue into the next trial phase (e.g., an unblinded extension).

6.7 Treatment exposure and compliance

Pharmacokinetic parameters (measures of treatment exposure) will be determined in all subjects treated with LHW090, as detailed in Section 8.5.

6.8 Recommended treatment of adverse events

Adverse events should be treated at the discretion of the Investigator based on his/her judgment and best medical practices. Medication used to treat AEs must be recorded on the Concomitant medications/Significant non-drug therapies CRF.

6.9 Rescue medication

Rescue medication to treat severe or serious conditions as per standard of care, at the discretion of the Investigator, is allowed. Use of rescue medication must be recorded on the Concomitant medications/Significant non-drug therapies CRF after start of study drug.

6.10 **Concomitant treatment**

All prescription medications, over-the-counter drugs, herbal medications and significant non-drug therapies (including physical therapy and blood transfusions) taken within the timeframe defined in the entry criteria prior to the start of the study and during the study, must be recorded on the Concomitant Medications/Non-drug therapies page of the eCRF.

Certain prescription, over-the-counter or herbal medications will not be allowed during the course of the study unless the patient has been on a standard treatment regimen for at least 30 days prior to first dosing and will continue their regular regimen without changes throughout the study (unless required to treat adverse events). Some of these medications may have to be discontinued, as per discussion with the sponsor. Please refer to Section 5.2 for prohibited treatments.

Due to the potential for pharmacokinetic drug-drug interactions, subjects taking statins should be monitored for statin-related myositis (e.g. muscle pain or elevations in creatinine kinase) during the duration of the study. Under the guidance of their treating physician, subjects on rosuvastatin may consider halving their dose or switching to another statin for the duration of the study.

The investigator should instruct the patient to notify the study site about any new medications (prescription or over-the-counter) he/she takes after the start of the study drug. Medication entries should be specific to trade name, the single dose and unit, the frequency and route of administration, the start and discontinuation date and the reason for therapy.

7 Discontinuation and study completion

7.1 **Discontinuation of study treatment**

Study treatment must be discontinued and the patient withdrawn from the study if the patient withdraws consent. Patients may voluntarily withdraw from the study for any reason at any time. They may be considered withdrawn if they state an intention to withdraw, fail to return for visits, or become lost to follow-up for any other reason. If a patient withdrawal occurs for any reason, the Investigator must make every effort to determine the primary reason for a patient's withdrawal from the study and record this information on the CRF.

The Investigator should discontinue study treatment for a given patient or withdraw the patient from study if on balance they believe that continuation would be detrimental to the patient's well-being. Under the following circumstances, individual study treatment must be discontinued and the patient monitored until resolution of the reason for discontinuation according to the Investigator's discretion:

- A reproducible and persistent (confirmed on repeat assessment within 24 48 hr) increase
 in serum creatinine ≥0.3 mg/dL from baseline. Any increases in serum creatinine
 ≥0.3 mg/dL based on local laboratory assessments should trigger repeat assessments of
 serum creatinine until event resolution (e.g. serum creatinine within 10% of baseline) or
 event stabilization. Baseline is defined as the average of all available pre-dose
 measurements.
- Systolic blood pressure <90 mm Hg (must be confirmed on repeat measurement after 30 minutes) or symptomatic hypotension
- Any protocol deviation (e.g. use of an ACE inhibitor) that results in a significant risk to the patient's safety

7.2 Study completion and post-study treatment

Each subject will be required to complete the study in its entirety and thereafter no further study treatment will be made available to them. Study completion is defined as when the last subject completes their End of Study visit, and any repeat assessments associated with this visit have been documented and followed-up appropriately by the Investigator, or in the event of an early study termination decision, the date of that decision.

At a minimum, subjects will be contacted for safety evaluations during the 30 days following the Study Completion visit, including a final post-study safety contact at the 30-day point after last visit. Documentation of attempts to contact the subject should be recorded in the source documentation.

7.2.1 Lost to follow-up

For subjects whose status is unclear because they fail to appear for study visits without stating an intention to discontinue or withdraw, the investigator should show "due diligence" by documenting in the source documents steps taken to contact the subject, e.g. dates of telephone calls, registered letters, etc. A subject should not be formally considered lost to follow-up until his/her scheduled end of study visit would have occurred.

7.3 Withdrawal of consent

Subjects may voluntarily withdraw consent to participate in the study for any reason at any time.

Withdrawal of consent occurs only when a subject does not want to participate in the study anymore **and** does not want any further visits or assessments **and** does not want any further study related contact **and** does not allow analysis of already obtained biologic material.

If a subject withdraws consent, the investigator must make every effort to determine the primary reason for this decision and record this information. Study treatment must be discontinued and no further assessments conducted. All biological material that has not been analyzed at the time of withdrawal must not be used. Further attempts to contact the subject are not allowed unless safety findings require communicating or follow-up.

7.4 Study Stopping rules

The study will be put on hold if any of the following criteria are met and no further dosing will occur pending a full safety review:

- 1 or more study-drug related SUSAR is reported
- 2 patients experience a systolic blood pressure <90 mm Hg that is persistent (>8 hours) and symptomatic and suspected to be related to the study drug
- 3 patients experience a doubling of their baseline serum creatinine (based on local laboratory assessments) that is suspected to be related to the study drug. Baseline is defined as the average of all available pre-dose measurements.
- 3 patients experience a similar AE which is assessed as moderate in intensity and is potentially related to the study drug

This study can continue if, after the review, the Investigator and Sponsor agree that it can safely continue.

The study may also be stopped at any time by the sponsor.

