3.6 Risks and benefits

There is no benefit expected for subjects participating in this study. In Part 1, patients will receive escalating doses of LHW090 four days. Corporate Confidential Information

over

Based on other compounds with a similar mode of action, low blood pressure may be a potential risk.

Corporate Confidential Information

An allergic-type reaction called angioedema has been reported with a compound with a similar mode of action as LHW090. This risk may be increased when LHW090 is taken concomitantly with an ACE inhibitor. Subjects who are unable to substitute an ACE inhibitor with an angiotensin receptor blocker are excluded from this study. Due to the potential for pharmacokinetic drug-drug interactions, subjects taking statins should be monitored for statin-related myopathy during the duration of the study. For further details, refer to the Investigator Brochure and Section 5.2 "Prohibited treatment".

The risk to subjects in this trial will be minimized by adherence to the eligibility criteria, individual and study stopping criteria, and close clinical monitoring. Clinical monitoring includes regular monitoring of renal function in an in-patient setting in Part 1.

Corporate Confidential Information

In Part 1, a maximum of 235 mL of blood is planned to be collected over a period of 7 weeks from each subject as part of the study. In Part 2, a maximum of 135 mL of blood is planned to be collected over a period of 9 weeks from each subject as part of the study. Additional samples for monitoring of any safety findings would be in addition to this. This is not considered to be a risk for this population.

There may be unknown risks of LHW090 which may be serious and unforeseen.

4 Population

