9.1 Adverse events

An adverse event (AE) is any untoward medical occurrence (i.e., any unfavorable and unintended sign [including abnormal laboratory findings], symptom or disease) in a subject or clinical investigation subject *after providing written informed consent* for participation in the study. Therefore, an AE may or may not be temporally or causally associated with the use of a medicinal (investigational) product.

The occurrence of adverse events should be sought by non-directive questioning of the subject at each visit during the study. Adverse events also may be detected when they are volunteered by the subject during or between visits or through physical examination, laboratory test, or other assessments.

Abnormal laboratory values or test results constitute adverse events only if they fulfill at least one of the following criteria:

- they induce clinical signs or symptoms,
- they are considered clinically significant,
- they require therapy.

Clinically significant abnormal laboratory values or test results should be identified through a review of values outside of normal ranges/clinically notable ranges, significant changes from baseline or the previous visit, or values which are considered to be non-typical in patients with underlying disease. Investigators have the responsibility for managing the safety of individual subject and identifying adverse events. Alert ranges for liver related events are included in Section 9.3.

Adverse events must be recorded on the Adverse Events CRF for subjects that pass screening and enter into the study. The adverse events should be reported according to the signs, symptoms or diagnosis associated with them, and accompanied by the following information:

- 1. the severity grade
 - mild: usually transient in nature and generally not interfering with normal activities
 - moderate: sufficiently discomforting to interfere with normal activities

- severe: prevents normal activities
- 2. its relationship to the study treatment (no/yes),
- 3. its duration (start and end dates) or if the event is ongoing an outcome of not recovered/not resolved should be reported.
- 4. whether it constitutes a serious adverse event (SAE) See Section 9.2 for definition of SAE
- 5. action taken regarding [study/investigational] treatment(select as appropriate).

All adverse events should be treated appropriately. Treatment may include one or more of the following:

- no action taken (i.e. further observation only)

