Liver events	ALT or AST > 5 × ULN
	 ALP > 2 × ULN (in the absence of known bone pathology)
	 TBL > 2 × ULN (in the absence of known Gilbert syndrome)
	 ALT or AST > 3 × ULN and INR > 1.5
	 Potential Hy's Law cases (defined as ALT or AST > 3 × ULN and TBL > 2 × ULN [mainly conjugated fraction] without notable increase in ALP to > 2 × ULN)
	Any clinical event of jaundice (or equivalent term)
	 ALT or AST > 3 × ULN accompanied by (general) malaise, fatigue, abdominal pain, nausea, or vomiting, or rash with eosinophilia
	 Any adverse event potentially indicative of a liver toxicity *

Table 9-2 Follow Up Requirements for Liver Events and Laboratory Triggers

Criteria	Actions required	Follow-up monitoring
Potential Hy's Law case ^a	 Discontinue the study drug immediately Hospitalize, if clinically appropriate Establish causality 	ALT, AST, TBL, Alb, PT/INR, ALP and γGT until resolution ^c (frequency at investigator discretion)
ALT or AST	Complete liver CRF	
> 8 × ULN	 Discontinue the study drug immediately Hospitalize if clinically 	ALT, AST, TBL, Alb, PT/INR, ALP and γGT until resolution ^c (frequency at investigator discretion)
	Hospitalize if clinically appropriateEstablish causality	,
	Complete liver CRF	
> 3 × ULN and INR > 1.5	Discontinue the study drug immediately	ALT, AST, TBL, Alb, PT/INR, ALP and γGT until resolution ^c (frequency at investigator discretion)
	Hospitalize, if clinically appropriate	at investigator discretion)
	Establish causalityComplete liver CRF	
> 5 to ≤ 8 × ULN	 Repeat LFT within 48 hours If elevation persists, continue follow-up monitoring If elevation persists for more than 2 weeks, discontinue the study drug Establish causality Complete liver CRF 	ALT, AST, TBL, Alb, PT/INR, ALP and γGT until resolution ^c (frequency at investigator discretion)
> 3 × ULN accompanied by symptoms ^b	 Discontinue the study drug immediately Hospitalize if clinically appropriate Establish causality Complete liver CRF 	ALT, AST, TBL, Alb, PT/INR, ALP and γGT until resolution ^c (frequency at investigator discretion)
> 3 to ≤ 5 × ULN (patient is asymptomatic)	 Repeat LFT within the next week If elevation is confirmed, initiate close observation of the patient 	Investigator discretion Monitor LFT within 1 to 4 weeks
ALP (isolated)		
> 2 × ULN (in the absence of known bone pathology)	 Repeat LFT within 48 hours If elevation persists, establish causality 	Investigator discretion Monitor LFT within 1 to 4 weeks or at next visit

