9.7 Early phase safety monitoring

The Investigator will monitor adverse events in an ongoing manner and inform the Sponsor of any clinically relevant observations. Any required safety reviews will be made jointly between medically qualified personnel representing the Sponsor and Investigator. Such evaluations may occur verbally, but the outcome and key discussion points will be summarized in writing (e-mail) and made available to both Sponsor and all Investigator(s). Criteria pertaining to stopping the study/treatment or adapting the study design are presented above.

When two or more clinical site(s) are participating in the clinical study, the Sponsor will advise the Investigator(s) at all sites in writing (e-mail) (and by telephone if possible) of any new, clinically relevant safety information reported from another site during the conduct of the study in a timely manner.

10 Data review and database management

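### The similar-adverse-event hold rule names only moderate events, so severe events do not count toward it as written

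*Protocol*

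**What the plan says.** Protocol section 7.4 sets study-level holds that are mandatory and last until a review is complete: "The study will be put on hold if any of the following criteria are met and no further dosing will occur pending a full safety" […]. There are four criteria:

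1. One or more drug-related SUSARs.
2. Two patients with "systolic blood pressure <90 mm Hg that is persistent (>8 hours) and symptomatic", suspected to be drug-related.
3. Three patients whose serum creatinine doubles from baseline, suspected to be drug-related.
4. "3 patients experience a similar AE which is assessed as moderate in intensity and is potentially related to the study drug".

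Section 9.1 grades every adverse event as mild, moderate or severe. The top grade reads "severe: prevents normal activities". Whether an event is serious is recorded as a separate item from its severity.

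Section 3.6 names hypotension as a possible class effect: "Based on other compounds with a similar mode of action, low blood pressure may be a potential risk".

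The SAP contains no visible text on stopping rules.

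**The concern.** The fourth criterion uses a grade label that the protocol itself defines, and it names one grade only. It does not say at least moderate, or moderate or severe. Followed exactly, the same cluster of three similar related events stops dosing when all three are moderate and does not when one or more are severe. That is the wrong direction for a safety rule.

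At stake is whether dosing of the remaining patients stops automatically. The population has moderate renal impairment, section 3.6 expects no benefit for participants, and section 10.4 plans no data monitoring committee.

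**Working it through.** **Step 1: does another hold criterion catch the severe events?**

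| Criterion in 7.4 | What a severe event also needs |
|---|---|
| SUSAR (1 case) | To be serious and unexpected. Section 9.1 records seriousness apart from severity, so a severe event need not be serious, and a serious expected event is not a SUSAR. |
| Blood pressure (2 patients) | SBP below 90 mm Hg, for more than 8 hours, with symptoms |
| Creatinine (3 patients) | A doubling from baseline |
| Similar AE (3 patients) | To be graded moderate |

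What escapes all four is a severe, related event that is non-serious, or serious but expected, and that meets neither the blood-pressure nor the creatinine rule.

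**Step 2: an example.** Take three patients with related hypotension that resolves within 8 hours. If all three are graded moderate, the count is 3 and the study is held. If two are moderate and one severe, the count is 2 and this criterion is not met. If all three are severe, the count is 0. In the last two cases there is a mandatory hold only if one of the events is a SUSAR.

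**Step 3: do the patient-level rules fill the gap?** Section 7.1 stops the affected patient for "Systolic blood pressure <90 mm Hg (must be confirmed on repeat measurement after 30 minutes) or symptomatic hypotension" and for a confirmed creatinine rise of at least 0.3 mg/dL. For several liver findings Table 9-2 requires "Discontinue the study drug immediately". These rules act on the affected patient and do not pause dosing in others. Section 9.7 says "Any required safety reviews will be made jointly between medically qualified personnel representing the Sponsor and Investigator", but it sets no numerical trigger and refers back to the criteria already given.

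**Step 4: illustrative size.** The plan states no figure here to reproduce. Inputs:

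- n = 54 active patients in Part 2 (section 11.6).
- p = the share of patients with a similar related moderate-or-severe event not caught by another criterion (assumed).
- s = the fraction of those events that are severe (assumed).

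With X the number of patients counted, P(X ≥ 3) = 1 − P(0) − P(1) − P(2) from the binomial distribution. The event probability is p if both grades count, and p(1 − s) under the literal wording.

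Worked case, p = 0.10 and s = 0.50:

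- Both grades count (probability 0.10): 1 − (0.0034 + 0.0203 + 0.0597) = 0.917.
- Literal wording (probability 0.10 × 0.50 = 0.05): 1 − (0.0627 + 0.1781 + 0.2484) = 0.511.

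| p | Both grades count | Literal, s = 25% | Literal, s = 50% | Literal, s = 75% |
|---|---|---|---|---|
| 5% | 51% | 33% | 15% | 3% |
| 10% | 92% | 78% | 51% | 15% |
| 15% | 99% | 95% | 78% | 33% |

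If no events are severe (s = 0), nothing is lost.

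**Step 5: sensitivity to the SUSAR route.** Now let a share q of the severe events be SUSARs (assumed), each of which alone holds the study. Then P(hold) = 1 − P(no SUSAR and at most 2 counted events). With n = 54, p = 10%:

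| s | q | Literal | Both grades count |
|---|---|---|---|
| 50% | 0 | 51% | 92% |
| 50% | 25% | 76% | 93% |
| 50% | 50% | 88% | 95% |
| 50% | 75% | 94% | 96% |
| 75% | 50% | 89% | 96% |

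The rule counts patients, and blinded investigators judge relatedness, so placebo cases could count too. With n = 72, p = 10%, s = 50% and q = 0, the figures are 70% and 98%.

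**The case against.** The best defence is that nobody would apply the literal reading. The drafters very probably meant at least moderate, and it is hard to imagine medically qualified staff pausing for three moderate cases but not for two moderate and one severe. Severe events also have a stricter route, since a single SUSAR holds the study and the SAE definition in section 9.2.1 is broad. Section 3.6 rests the hypotension risk on other compounds, so the visible text does not show that severe hypotension would count as expected. The sponsor-open design in section 3.2 was chosen partly for earlier detection of safety problems, and the sponsor may stop the study at any time. Redacted text might hold a further trigger.

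Much of this stands as mitigation. The SUSAR route shrinks the gap: at p = 10% and s = 50% the difference falls from 41 percentage points with q = 0 to about 2 points with q = 75%. The Step 4 table is therefore conditional on events that no other criterion catches, and is not a forecast of how often the study would fail to be held.

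It does not remove the point. Probable intent is not text, and section 9.7 allows for two or more sites, so a mandatory trigger should not depend on interpretation. The other safeguards are discretionary or apply to one patient. Redacted text cannot be assessed, and the criteria in 7.4 and the grades in 9.1 are legible.

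**Conclusion.** The concern holds as a bounded gap in a mandatory rule. As worded, two moderate plus any number of severe, similar, related, non-SUSAR events do not meet the fourth criterion. This conclusion rests on the text of sections 7.4 and 9.1 alone.

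The size depends on assumed rates. For events outside the other criteria, the loss in the chance of a hold ranges from nothing when no event is severe to 77 percentage points (92% to 15%) at a 10% rate with three quarters severe. It is smaller wherever some severe events are SUSARs. The finding does not show that severe events would be ignored in practice. It shows that the protocol does not make the hold automatic for them. The change should be made.

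**What to change.** In the fourth criterion of section 7.4, replace *moderate in intensity* with *moderate or severe in intensity*. The sponsor's clinicians may also want a lower count for severe events. That is a clinical choice and is not needed to close the gap.

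The cost is two added words in a protocol amendment. No endpoint, analysis or sample size changes. The downside is an occasional additional hold and safety review, which section 7.4 already lets the investigator and sponsor end once they agree the study can safely continue.
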